#### **6) Data and Specimen Banking\***

All subjects will undergo laboratory assessment (sodium, potassium, chloride, bicarbonate, blood urea nitrogen, creatinine, glucose, aspartate aminotransferase, alanine aminotransferase, total bilirubin, direct bilirubin, alkaline phosphatase, lipase, amylase) before starting teduglutide and subsequent laboratory tests will be performed as stated in the schedule below. These labs are normally drawn during the course of clinical care.

Specifically, the labs which will be assessed in this study are:

Total bilirubin ( normal 0.0 – 1.0 mg/dL)

Alkaline phosphatase (normal 45 -115 U/L)

Lipase (normal 13 – 60 U/L)

Creatinine (normal 0.6-1.5 mg/dL)

#### **Data Fields**

Age

BMI

Gender

Charlson Comorbidity Index

Questionnaires (see additional documents)

Cause of major intestinal resection: trauma, emergency operation, elective operation, inflammatory bowel disease, other

Location of fistula: stomach, duodenum, jejunum, ileum, colon

Days since last operation

Days since fistula diagnosis

Type of nutrition: per os (PO), enteral nutrition (EN), parenteral nutrition (PN), PO + EN, PO + TPN, EN + PN, PO +EN + PN

IRB Study Number: 20170189  
Version Date: June 16, 2021  
PI: [name]

NCT02889393

Concomitant medications: antidiarrheals, antisecretory agents  
3-day average fistula volume (continuous variable)  
Output of fistula >500 mL/day (Y/N)

Because of the expected increase in luminal absorption, subjects will be closely monitored for increased oral medication absorption, particularly opioids and sedating medications. Subjects will be assessed for pinpoint pupils and lethargy. If clinical evidence of increased oral medical absorption is discovered, the doses will be accordingly decreased. If clinical evidence of fluid overload is discovered (such as breathlessness, subjective dyspnea, new-onset pitting peripheral edema, change in body weight, jugular venous distention, and rales on lung auscultation), then EN and PN prescription will be decreased accordingly.

Additionally, subjects will be monitored for clinical evidence of volume depletion. Clinical signs suggestive of volume depletion include dry mucus membranes, poor skin turgor, decreased urine output, or rapid body weight loss.

Fluid and volume status will be assessed according to the usual clinical signs and symptoms: breathlessness, subjective dyspnea, new-onset pitting edema, change in body weight, and rales on lung auscultation. This will be assessed both in person at the time of study visit as well as by self report from the subject during phone calls.

Criteria for discontinuation of teduglutide in patients who experience fluid overload include: decrease in room-air oxygen saturation > 5% from baseline, significant worsening of peripheral edema resulting in functional limitation, severe dyspnea resulting in functional limitation, and hospitalization for congestive heart failure.

Data will be de-identified and stored on password-protected network accessible only to research staff. Data will be retained for at least six years following conclusion of the study on this network.

## **7) Biostatistical Analysis**

Because this is a pilot study enrolling only 10 subjects, no sample size or power calculation was performed. The primary endpoint (decrease in fistula volume by 20%) was chosen based on previous studies in a different population.

Continuous outcome variables that are normally distributed will be presented as mean  $\pm$  Standard Deviation (SD) while continuous outcome variables that are not normally distributed will be presented as median and interquartile range (IQR). In calculating the difference in fistula volume between baseline and final measures, a two-sample t-test for independent samples will be used. A p value of <0.05 will be considered significant.

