**Design**

Open label cross-over pilot study to determine safety and efficacy of teduglutide in patients with ECF. Our planned sample size is 10 subjects randomized and treated with at least 1-dose of study drug .

IRB Study Number: 20170189  
Version Date: June 16, 2021  
PI: [name]

NCT02889393

The primary efficacy end point will be decrease in fistula volume by 20% from baseline 3-day average, as measured by the patient.

The secondary efficacy end points will be cessation of fistula output altogether and health-related quality of life questionnaire score as assessed by the questionnaires (see below) at time points Study Visit 5, 10, and 11 (3 months after end-of-treatment).

Subjects that complete both arms of the study who have a favorable (but incomplete) response and are deemed to be reliable (both as determined by the principal investigator) will be offered an open-label extension during which they will continue to receive teduglutide for up to another 12 months or permanent fistula closure, whichever occurs first.

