additional patients achieving PN/IV independence. Of the 19 non-responders in the original 24-week study, 11 became responders in the extension study [11]. Approved by the FDA in 2012 for the treatment of adults with short bowel syndrome with intestinal failure (SBS-IF), teduglutide is well-tolerated and common adverse events are mild and related to gastrointestinal symptoms such as abdominal pain, nausea, and vomiting [12].

It is easy to conceive that the results of teduglutide treatment could be extrapolated to patients with ECF. For example, SBS-IF patients treated with GLP-2 experienced a reduction in fecal wet weight of approximately 33% (from 3.0 kg/day to 2.0 kg/day) [7]. Similar changes in ECF could convert high-output fistulas (>500 mL/day) to medium- (200-500 mL/day) or low-output fistulas (<200 mL/day), significantly simplifying fluid/electrolyte management, or even resolve low-output fistulas completely.

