### **10) Potential Benefits to Subjects**

Based on the encouraging results in studies of teduglutide for patients with short bowel syndrome, we expect a clinically significant decrease in daily ECF volume of about 20% magnitude. This could convert high-output fistulas (>500 mL/day) to medium- (200-500 mL/day) or low-output fistulas (<200 mL/day), significantly simplifying fluid/electrolyte management, allow for liberation from parenteral nutrition, or even resolve low-output fistulas completely. It is reasonable to expect an improvement in quality of life.

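### Fistula volume is tested with a t-test whatever its distribution; with 10 patients the largest fistulas can dominate the mean change, and a within-patient rank test on a pre-specified scale would guard against this

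*Combined protocol and SAP*

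**What the plan says.** Section 7 (Biostatistical Analysis) gives one inferential rule for fistula volume: "In calculating the difference in fistula volume between baseline and final measures, a two-sample t-test for independent samples will be used". It adds: "A p value of <0.05 will be considered significant". The same section foresees skewed data, but only for description: "continuous outcome variables that are not normally distributed will be presented as median and interquartile range (IQR"). No transformation, percent-change analysis or rank test is named. Section 6 (Data Fields) lists the 3-day average volume as a continuous variable.

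The endpoint itself is relative. Under Design: "The primary efficacy end point will be decrease in fistula volume by 20% from baseline 3-day average, as measured by the patient". The secondary endpoints there include complete cessation of output, which is a volume of zero.

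On spread, section 3 (Background) hopes that treatment could "convert high-output fistulas (>500 mL/day) to medium- (200-500 mL/day) or low-output fistulas (<200 mL/day"), and section 10 repeats these classes. Section 4 (Entry Criteria) puts no lower or upper limit on output. On size, section 7 says: "Because this is a pilot study enrolling only 10 subjects, no sample size or power calculation was performed".

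**The concern.** A uniform 20% fall is 20 mL in a patient draining 100 mL/day and 200 mL in one draining 1,000 mL/day. A mean change in mL therefore weights patients by fistula size, which is not how the endpoint is defined. In a sample of 10, one large fistula can supply much of the mean and most of the standard deviation. A consistent proportional response could then miss p<0.05, or one large fistula that worsens could hide many that improve. The plan recognises that the data may not be normal, yet provides no other test. Correcting the lack of pairing alone would probably lead to a paired t-test on mL, which keeps this weakness.

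**Working it through.** **Inputs from the documents.** n = 10; significance at p<0.05 (sidedness not stated, two-sided assumed); effect 20%; output classes <200, 200-500 and >500 mL/day; no entry limit; zero possible. There is no mean, SD or upper value for output and no power calculation, so there is no planned figure to reproduce.

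**Assumptions, not in the documents.** Baselines are lognormal with median 400 mL/day and CV 60, 100 or 150%. The log-scale SD is s = √ln(1+CV²) = 0.555, 0.833, 1.086, which puts 11/20/26% of patients below 200 and 34/39/42% above 500 mL/day.

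**Step 1: leverage, with ten illustrative baselines** (100, 150, 200, 300, 400, 500, 700, 1,000, 1,500, 2,500; sum 7,350).

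All ten fall 20%:
- Mean change = 0.2 × 735 = 147 mL. The top two supply (1,500 + 2,500)/7,350 = 54% of it.
- Planned independent-samples test: SDs 757 and 606, SE = √((757² + 606²)/10) = 307, t = 147/307 = 0.48, p = 0.64.
- Paired t-test on mL: SD of change 151, SE = 151/√10 = 48, t = 3.07, p = 0.013.
- Exact signed-rank, either scale: p = 2/2¹⁰ = 0.002.

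Nine fall 30% and the largest rises 20%:
- Mean change = -95.5 mL, SD 246.5, t = 95.5/(246.5/√10) = 1.23, paired p = 0.25. The planned test gives p = 0.80.
- Signed-rank on percent change: the single rise has the smallest rank, p = 4/1,024 = 0.004.
- Signed-rank on mL: the single rise (500 mL) has the largest rank, p = 86/1,024 = 0.084. Ranking mL limits one patient's influence but does not remove it.

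**Step 2: power as written.** In simulation with the same patients in both samples, the independent-samples test has about 0-1% power on raw mL and about the same on the log scale. Changing the scale alone recovers almost nothing until the analysis is within-patient. If the sentence is instead read as 5 versus 5 on change from baseline (log-scale SD 0.6/0.8/1.0 between patients and 0.15 within), raw mL gives 20/16/13% against 30-32% on the log scale.

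**Step 3: within-patient power, error proportional to output** (true ratio 0.8, SD of log-ratio 0.2, no closures):

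| Test | CV 60% | CV 100% | CV 150% |
|---|---|---|---|
| Paired t, mL | 75% | 62% | 47% |
| Signed-rank, mL | 79% | 77% | 74% |
| Signed-rank, percent change | 82% | 83% | 82% |

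At CV 100% the rank test on mL gains 77 - 62 = 15 of the 83 - 62 = 21 points available, so most of the gain comes from ranking rather than from leaving mL. With log-ratio SD 0.3, the paired t-test gives 39/32/24% and signed-rank on percent change 44/46/45%.

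**Step 4: zeros.** With 10% closures at CV 100%, power is 57-59% (paired t, mL) against 86-87% (signed-rank, percent change) at SD 0.2, and 34-35% against 55% at SD 0.3. A log transform is not a safe remedy: in a parallel model (within-patient log SD 0.15), a paired t-test on log(x+10) fell to 36% with 10% closures.

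**Step 5: error constant in mL** (SD of the difference 40, 75, 100 or 150 mL). With the error in the final value only, signed-rank on percent change loses about 5 to 19 points to the paired t-test on mL. With error in both measurements, so that it also enters the denominator, the loss is larger. At CV 100% the figures are 93/76/63/41% against 79/51/37/22%, a gap of 14, 25, 26 and 19 points. Signed-rank on mL loses at most about 1 to 2 points.

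**Step 6: no true change.** Rejection was 2.3-4.1% for the paired t-test on mL and 4.6-5.6% for signed-rank.

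**The case against.** The strongest reply is that the advantage of percent change is built into the error model. If noise scales with output, percent change must do well. Volume is measured by the patient as a 3-day average, and an error that is partly constant in mL is equally plausible. Step 5 shows that the ranking then reverses, because low-output patients with small denominators dominate the percent scale. This stands. A reader might infer that mL should become purely descriptive, or that moving to percent change costs only a few points of power. The documents do not support either, since they contain no data on measurement error.

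A second reply is that pairing matters far more. That also stands: this point has practical effect only once the analysis is within-patient.

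A third is that this is a pilot with no power promise, and that the inputs are assumed. Both are true, and at CV 60% the gain from ranking mL is only about 4 points. But the plan sets a p<0.05 rule and aims to demonstrate efficacy, and with 10 patients the dependence on the largest fistulas affects the estimate as well as the p-value.

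**Conclusion.** The point holds in a limited form. The plan uses a normal-theory test regardless of distribution and names no scale for a relative endpoint. After pairing is corrected, the cost of keeping a t-test on mL runs from about 4 points (CV 60%) to 27 points (CV 150%, 74 - 47) against signed-rank on mL under proportional error. Under constant error there is little or nothing to lose by ranking. The further step to percent change adds 3 to 8 points (82 - 79 to 82 - 74) under proportional error, and can cost 5 to 19 or more under constant error.

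Three stronger readings should be avoided:
- **Inflated false positives.** The null runs show the t-test on mL to be conservative; the loss is of power and interpretability.
- **Stated scale and spread.** The plan does not say raw mL or give any output range above 500 mL/day. Both are inferences, from the wording of the test and from the output classes with no entry limit.
- **Scale as the main fault of the planned test.** The independent-samples form is.

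Every power figure is conditional on the assumed distributions.

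**What to change.** Amend section 7 before the data are analysed:

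- Make the comparison within-patient.
- Replace the t-test with an exact Wilcoxon signed-rank test, or a sign-flip permutation test of a rank-based or otherwise robust statistic. Permuting the mean mL change would keep the leverage problem.
- Pre-specify one scale for the p-value and make the other a sensitivity analysis. mL is the safer choice across both error models; percent change is closer to the endpoint and stronger if error is proportional.
- Report the Hodges-Lehmann median percent change from own baseline, with closure as -100% and a 95% CI, as the estimate matching the endpoint.
- State how ties and zero differences are handled, and use the same approach for any treatment comparison.

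The cost is SAP wording; no new data are needed. There are three downsides. The first is the possible loss on the percent scale shown in step 5. The second is that a p-value in mL and an interval in percent may disagree, so the plan should say which governs. The third is that an exact two-sided signed-rank test cannot reach p<0.05 with fewer than six non-zero pairs (five pairs: 2/2⁵ = 0.063; six: 2/2⁶ = 0.031), which matters if several patients lack a final measure.

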### **Enrollment within 2 months of signing consent**

Inclusion/Exclusion criteria

Vital signs measurements

Nutritional assessment

3-day average fistula output

Complete questionnaires (see additional documents):

1. ASCQ-Me Short Form v2.0 - Social Functioning Impact
2. ASCQ-Me v2.0 - Sleep Impact Short Form

IRB Study Number: 20170189  
Version Date: June 16, 2021  
PI: [name]

NCT02889393

3. Global Health Scale v1.2
4. PROMIS Scale v1.0 - GI Belly Pain
5. PROMIS Scale v1.0 - GI Diarrhea
6. PROMIS Scale v1.0 - GI Nausea and Vomiting
7. PROMIS SF v2.0 - Ability to Participate

Teaching of self-administration of medication

After study enrollment, the subject will be randomly assigned (by a computerized method, using the site 'www.sealedenvelope.com') to begin teduglutide treatment immediately or to continue standard of care (SOC) treatment. The randomization will be performed by a member of the study that is not involved in the informed consent process, and will be enclosed in sequentially numbered opaque envelopes. The envelopes will be given to the PI prior to the enrollment visit. At study visit 5 (day 56), the subject will then cross-over to the opposite treatment assignment. The half-life of teduglutide is 2-3 hours. During the period the subjects are on the "SOC only" treatment arm, the subjects will be given the option to replace some Study visits with Telephone Calls for their convenience. If study visits overlap due to the time window, either visit may be skipped or completed on the same day. Please see information below, and the Study schema.

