**Study Visit 10, End of Treatment (EOT), (Day 112) (+/- 1 week)**

Collect physical examination  
Collect Vital Signs measurements  
Chemistry Panel (sodium, potassium, chloride, bicarbonate, blood urea nitrogen, creatinine glucose)  
Liver Function tests (total bilirubin, direct bilirubin, alkalkine phosphatase, alanine aminotransferase, aspartate aminotransferase, lipase, amylase)  
Plasma PK (Pharmacokinetics)

- Processed according to separate "Sample Processing Procedure"

Serum pregnancy test  
Monitor severe adverse events (SAE) and adverse events (AE)  
Collect Concomitant medication review  
Collect Nutritional Assessment  
3-day average fistula volume (3 days immediately preceding study visit)  
Collect adjustment of medications and fluids if recorded  
Fistula closure (y/n)  
Complete Questionnaires (see additional documents)

IRB Study Number: 20170189  
Version Date: June 16, 2021  
PI: [name]

NCT02889393

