**Study Visit 11, Long-Term Follow-up Visit, 3 months after EOT (-2 weeks/+3 months)**

Monitor severe adverse events (SAE) and adverse events (AE)

Collect Concomitant medication review

Collect Nutritional Assessment

Chemistry Panel (sodium, potassium, chloride, bicarbonate, blood urea nitrogen, creatinine glucose)

Liver Function tests (total bilirubin, direct bilirubin, alkalkine phosphatase, alanine aminotransferase, aspartate aminotransferase, lipase, amylase)

Plasma PK (Pharmacokinetics)

- Processed according to separate "Sample Processing Procedure"

3-day average fistula volume (3 days immediately preceding study visit)

Fistula closure (y/n)

Complete Questionnaires (see additional documents)

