**Drug Administration, Dispensation and Disposition**

Once consent is obtained and necessary baseline data collected, the subject will begin receiving teduglutide (0.05 mg/kg/d, for moderate renal impairment defined as serum

IRB Study Number: 20170189  
Version Date: June 16, 2021  
PI: [name]

NCT02889393

creatinine > 1.5 times the upper limit of normal, the dose will be reduced to 0.025 mg/kg/d, administered once daily subcutaneously into the abdomen, thigh, or arm (at approximately the same time each day) for 8 weeks. For enrolled subjects demonstrating a favorable trend and are deemed to be reliable (both as determined by the PI) but still have a fistula at the end of treatment (EOT) or long-term follow-up, the subject will be offered an “open-label” extension whereby they will continue to receive teduglutide at the previous dose for up to another 12 months or permanent fistula closure, whichever occurs first.

Immediately prior to initiating the 8-week period of drug administration, the subject will receive training on how to safely reconstitute and administer the medication. The volume of reconstituted study drug to be administered is a fixed dose of 0.005 mL/kg body weight. Each day, the injection site should be changed. The subject should be dosed at approximately the same time each day. If a subject forgets to take drug, that day’s dose should be administered as soon as possible, even if this is later in the day or evening. Consecutive doses should be separated by approximately 12 hours. Dates of days with missed or incomplete doses are to be reported in the diary. The subject is going to be instructed to bring back all used and unused IP. The IP will then be disposed of per pharmacy SOP. University of Miami Research Pharmacy will be receiving, storing, dispensing, keeping inventory, and disposing the IP for this study as per their standard operating procedures.

Study drug will be packaged, labeled, and delivered to the clinical center by the sponsor or designee. Each study drug kit will contain labeling with the general dosage instructions, storage conditions, expiration date, kit number, and company name. All medication supplied to be used in this study will be manufactured, tested, labeled, and released according to current legal requirements and Good Manufacturing Practice (GMP). Ancillary supply kits containing syringes with needles for injection and reconstitution, sterile water, and alcohol swabs will also be provided.

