Because of the laboratory safety monitoring, the subjects will require blood draws before teduglutide initiation, at the mid-point of treatment (week 4), after the completion of the 8 week trial, and at long-term follow up (3 months after end of treatment). Patients with persistently abnormal laboratory results and ongoing adverse reactions will be followed until resolution and will undergo repeat laboratory testing as necessary to ensure resolution of all abnormal laboratory results potentially attributable to study drug. For patients receiving parenteral nutrition, this will not impact them as they will be getting test performed as part of routine care. However, for patients not requiring parenteral nutrition, this entails additional minimal blood loss and the discomfort of needle stick.

The most common adverse events identified in the previous trial (Jeppesen 2012, Teduglutide reduces need for parenteral support among patients with short bowel syndrome with intestinal failure) are mild and related to gastrointestinal symptoms such as abdominal pain (31%), nausea (29%), and abdominal distension (21%).

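### The randomised SOC data are never used as a comparator: the only planned test and the primary endpoint set an undefined final value against baseline

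*Combined protocol and SAP*

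**What the plan says.** Section 5 (Enrollment) randomises each patient to start teduglutide at once or to stay on SOC. Then: "At study visit 5 (day 56), the subject will then cross-over to the opposite treatment assignment". Three-day average output is recorded at every scheduled visit and call in both 8-week periods, and again at Visit 11.

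The primary efficacy endpoint in the Design section is a "decrease in fistula volume by 20% from baseline 3-day average". No visit, period or comparator is attached to it. Section 7 names a single hypothesis test: for the "difference in fistula volume between baseline and final measures", "a two-sample t-test for independent samples will be used", with significance at p<0.05. *Final* is not defined. No section mentions a teduglutide-versus-SOC contrast or a period, sequence or carry-over term.

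The Drug Administration part of Section 5 says that SOC runs alongside teduglutide. It lists infection control, nutritional support, fluid management and sometimes surgical repair as parts of SOC.

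**The concern.** The design creates a randomised control that the analysis does not use as a control. Two gaps combine.

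*Final* can be read in several ways:

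1. Day 112 (Visit 10). It is labelled end of treatment for everyone, although teduglutide-first patients have by then had 8 weeks of SOC only.
2. Visit 11, about 3 months later.
3. The end of each patient's teduglutide course, measured from enrolment.
4. The change across each patient's own course. Two places read as if there were one 8-week course for all: "Once consent is obtained and necessary baseline data collected, the subject will begin receiving teduglutide" in Section 5, and the Section 8 blood draws "at the mid-point of treatment (week 4), after the completion of the 8 week trial".

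Day 56 for everyone is a further candidate. *Baseline* is open too, because 3-day output is taken at both screening and enrolment.

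On every one of these readings, change under SOC is part of the result. A fall under SOC is credited to teduglutide, and a rise hides a real effect. The stated aim in Section 2 is to demonstrate efficacy, and neither the endpoint nor the test can separate the drug from the care given with it.

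Separately, if the two samples are baseline and final values of the same patients, an independent-samples test is the wrong test for them.

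**Working it through.** **Inputs from the documents.** 10 patients, swap at Day 56, end of period 2 at Day 112, Visit 11 nominally 13 weeks later, 20% threshold, p<0.05. Section 7 says that no sample size was calculated, so there is no planned figure to reproduce.

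**Assumptions (not in the documents).** 5 patients per sequence; two-sided tests; log-normal output; between-patient log-SD 0.2–0.8; within-patient log-SD *s* of a 3-day mean 0.15–0.35; fall per 8 weeks *n* on either treatment; drug effect *e*; carry-over share *c*. The value *n* = 10.6% was picked because two periods then give 20%, so 5% and 15% are shown beside it.

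**Step 1. Apparent fall with no drug effect (no SD needed).**

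| Meaning of *final* | Formula | n=5% | n=10.6% | n=15% |
|---|---|---|---|---|
| Day 112 | 1−(1−n)² | 9.8% | 20.1% | 27.8% |
| End of teduglutide, from enrolment | 1−[(1−n)+(1−n)²]/2 | 7.4% | 15.3% | 21.4% |
| Own course | n | 5% | 10.6% | 15% |
| Visit 11 (16+13 weeks) | 1−(1−n)^(29/8) | 17.0% | 33.4% | 44.5% |

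Example: 1−0.894² = 1−0.799 = 20.1%. A single fistula closing under SOC, with the others unchanged, adds 100%/10 = 10 points to the mean percentage fall.

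**Step 2. Rising output, true 20% effect.** At the end of teduglutide, 1−0.8×[(1+r)+(1+r)²]/2 gives 13.9% for r=5% and 6.8% for r=10.6%.

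**Step 3. Share of patients meeting the 20% criterion with no drug effect.** After k periods this is Φ[(ln 0.8 − k·ln(1−n))/(s√2)], averaged over k=1 and 2 because half the patients finish teduglutide in each period. For n=10.6% and s=0.15: Φ(−0.52)=0.30 and Φ(0.00)=0.50, mean 40%. Over s = 0.15–0.35:

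| No drift | 5% | 10.6% | 15% |
|---|---|---|---|
| 15–33% | 25–38% | 40–46% | 52–54% |

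The same shares apply at the end of SOC.

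**Step 4. Dilution at Day 112, true 20% effect, no drift.** 1−(0.8^c+0.8)/2 gives 10%, 15% and 20% for no, half and full carry-over.

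**Step 5. Significant results with no drug effect (simulation, 40,000 trials per cell, log scale).**

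| Test | n=5% | n=10.6% | n=15% |
|---|---|---|---|
| Planned independent test, Day 112 | 0.01–5.8% | 0.07–47% | 0.7–88% |
| Paired test, Day 112 | 9–28% | 25–84% | 45–99% |
| Paired test, own course | 6–11% | 10–32% | 15–58% |

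A period-adjusted crossover contrast stays at about 5% throughout. Correcting the pairing alone therefore raises the false-positive rate when there is drift. With a true 20% effect and no drift, the planned test at the end of teduglutide has 0.07–47% power, depending mainly on between-patient SD.

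**Step 6. The alternatives on the %-of-baseline scale, true 20% effect.**

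| Contrast | Carry-over | Estimate (points) | Power |
|---|---|---|---|
| Crossover | none | 20–23 | 20–81% |
| Crossover | half | 15–17 | 14–58% |
| Crossover | full | 10–11 | 9–33% |
| Day 56 between groups | not affected | 20–23 | 8–30% |

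The typical 95% half-width is 14–39 points for the crossover and 28–73 for Day 56. With no drug effect, both reject in 4–5% of trials.

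**The case against.** The strongest reply is that the two independent samples could be the two randomised sequences, with change from baseline compared between them. At Day 56 that would be a valid teduglutide-versus-SOC test. But the sentence names baseline and final measures and no groups, and it gives no time. At Day 112 the same comparison would no longer contrast drug with SOC, because each sequence has by then had both. What stands is that *no role* means no specified role as comparator. SOC-period values can still enter as final values.

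Second, the high error rates of the planned test need a small between-patient SD. A log-SD of 0.2 around an assumed 500 mL/day puts 95% of patients between about 340 and 740 mL, whereas the Background speaks of outputs from below 200 to above 500 mL/day. At 10.6% drift the planned test rejects in about 6–7% of trials at SD 0.4, and in under 1% at SD 0.8. This stands: over much of the range the main fault of the test as written is lost power. The bias in the estimate and in the responder rate does not depend on between-patient SD.

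Third, drift is assumed. That is so, but its absence is equally undocumented, and it may go either way. The Visit 11 row of Step 1 also ignores the open-label extension offered after Day 112. With no drug effect that changes nothing, but with a real effect it mixes treated and untreated patients further.

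Fourth, this is a 10-patient pilot with safety, feasibility and quality of life among its aims, and the crossover may suffer carry-over. Both points are fair. No analysis here is confirmatory. Even so, the plan sets a significance rule and an aim to demonstrate efficacy, and an estimate without a comparator cannot inform a next trial.

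**Conclusion.** The concern holds and should be fixed before analysis. That change under SOC is counted as drug effect follows from the text and the design alone. Its size rests on assumed drift: about 5–28% apparent fall with no drug effect across the Day 112, end-of-teduglutide and own-course readings, for falls of 5–15% per 8 weeks. Even without drift, 15–33% of patients would meet the 20% criterion through measurement noise, so a responder rate without its SOC counterpart cannot be interpreted. The loss at Day 112 (10% seen for a true 20%) assumes no carry-over and disappears if carry-over is complete.

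**What to change.** In Section 7 and the endpoint wording in the Design section:

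1. Define two values per patient, end of teduglutide and end of SOC (Day 56 or Day 112 according to sequence). State whether the screening or the enrolment 3-day average is baseline.
2. Replace the baseline-versus-final t-test with a teduglutide-versus-SOC comparison. Report, each with a 95% CI, the crossover contrast (the Day 56 minus Day 112 difference, compared between sequences and halved) and the baseline-adjusted Day 56 comparison between groups. Name one in advance as main and say why: the crossover is more precise, Day 56 is free of carry-over, and either is defensible. Use a scale that accepts a closed fistula (0 mL), such as % of baseline.
3. Report the proportion with a fall of at least 20% separately for the teduglutide and SOC periods.
4. Keep baseline-to-final change as descriptive only, with *final* defined. State that Day 112 is the end of period 2, and not the end of drug for teduglutide-first patients.

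The cost is wording only, with no new visits or data. The plan should say openly that there is no washout, that the trophic effect described in Section 3 or a fistula closure may outlast dosing despite the short half-life, and that the Day 56 comparison is too imprecise to rule carry-over out.
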